4.2 Inclusion Criteria

- 4.2.1 Participant provides informed consent prior to initiation of any study procedures.
- 4.2.2 Individual 18 to 75 years of age.
- 4.2.3 Documentation of confirmed active SARS-CoV-2 infection, as determined by an FDA authorized molecular test conducted at any US clinic or laboratory that has a Clinical Laboratory Improvement Amendments (CLIA) certification or its equivalent from any respiratory specimen collected <96 hours prior to study entry.
- 4.2.4 Mild or Moderate COVID-19 experiencing at least one SARS-CoV-2 infection symptom including:

Mild Covid-19

- Symptoms of mild illness with COVID-19 that could include fever, cough, sore throat, malaise, headache, muscle pain, gastrointestinal symptoms, without shortness of breath or dyspnea

Moderate Covid-19

- Symptoms of moderate illness with COVID-19, which could include any symptom of mild illness or shortness of breath with exertion
- Presence of clinical signs consistent with moderate illness with COVID-19, such as respiratory rate \geq 20 breaths per minute, saturation of oxygen (SpO2) $>$ 93% on room air at sea level, heart rate \geq 90 beats per minute from a health care encounter within 48 hours.

- 4.2.5 Agrees to not participate in another clinical trial for the treatment of COVID-19 or SARS-CoV-2 during the study period up until reaching hospitalization or 28 days, whichever is earliest.
- 4.2.6 Agrees to not utilize TCM outside of this study.
- 4.2.7 Willing to be randomized to XFBD and placebo control arm for 14 days, and followed up to 12 weeks.
- 4.2.8 Willing to comply with the study related questionnaires, procedures and measurements.
- 4.2.9 Will to not become pregnant during the 14 days of test substance ingestion using appropriate accepted methods of contraception. Acceptable methods of contraception include: postmenopausal 1 year of amenorrhea and over 50 years of age; prior tubal ligation or hysterectomy; or barrier contraception using condom or diaphragm plus spermicide.
- 4.2.10 Able to provide the identity of their health care provider or health system clinical care entry information.
- 4.2.11 Able to utilize telephone and telehealth platform to comply with the study related questionnaires, procedures and measurements. Established during the recruitment process.
- 4.2.12 Able to speak and communicate in English, Spanish, Mandarin Chinese or Cantonese.

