7 ADVERSE EVENTS AND STUDY MONITORING

7.1 *Definition of Adverse Events*

An AE is any unfavorable and unintended sign, symptom, or diagnosis that occurs in a study participant during the conduct of the study REGARDLESS of the attribution (i.e., relationship of event to medical treatment/study product/device or procedure/intervention). This includes any occurrence that is new in onset or aggravated in severity or frequency from the baseline condition.

Information sources include study assessments including daily and weekly PRO of telephone calls; health information obtained from the patients' health care providers and health system encounters including outpatient visits, urgent care, emergency room or inpatient visits.

Review by the study coordinator and medical monitor will be performed and those deemed a clinically significant worsening from baseline will be documented as an AE.

A clinically-significant finding could include: worsening from baseline (eg, by at least 1 grade); concomitant signs or symptoms related to the abnormal study assessment; further diagnostic testing or medical/surgical intervention required; if study drug is withheld, or discontinuation from study drug. Determination of clinical significance must be made by the medical monitor.

Events that do not meet the definition of an AE or SAE include: planned hospital admissions or surgical procedures for a condition that existed before the subject signed the informed consent are not to be considered AEs unless the condition deteriorates in an unexpected manner during the study (eg, surgery had to be performed earlier than planned); anticipated day-to-day fluctuations of pre-existing disease(s), condition(s), and signs or symptoms present or detected prior to the start of the study that are not more severe than expected for the subject's condition; and worsening of the COVID-19 including hospitalization, or death due to COVID-19.

7.2 *Adverse Event Collection Requirements for This Protocol*

Post-entry, all AEs must be recorded on the eCRFs **within 72 hours** if any of the following criteria have been met:

- All Grade ≥ 2 AEs
- All AEs that led to a change in study treatment/intervention regardless of grade
- All AEs meeting SAE definition

Serious Adverse Events (SAEs)

An SAE is defined as any untoward medical occurrence that:

- Results in death
- Is life-threatening illness
- Requires inpatient hospitalization or prolongation of existing hospitalization

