7.3. Relationship to Study Drug

Investigators should use their knowledge of the subject, the information from the patients health care providers and the circumstances surrounding the event, and an evaluation of any potential alternative causes to determine whether or not an AE is considered to be related to study drug, indicating on the eCRF that an AE is either related or unrelated. The following guidance should be taken into consideration when determining the relationship of an AE to study drug:

- Temporal relationship of event onset to initiation of study drug
- Course of the event, considering especially the effects of dose reduction, discontinuation of study drug, or reintroduction of study drug (where applicable)
- Known association of the event with study drug or with similar treatments
- Known association of the event with the disease under study
- Presence of risk factors in the subject or environment, or use of concomitant medications known to be associated with the event
- Presence of treatment-unrelated factors that are known to be associated with the occurrence of the event
- Whether there is a reasonable alternative explanation for the event

All AEs (including SAEs) will be assessed for the relationship of the AE to the study drug using the following definitions: not related; unlikely; possibly; probably; or definitely. For reporting and data analysis purposes, AEs reported with a causality assessment of “Definitely”, “Probably”, and “Possibly” are to be considered as “having a reasonable causal relationship” to study drug.

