8.2 Potential Toxicities

The side effects which are described with the components of the XFBD are listed in Table 8.2.

Table 8.2 Side Effects of the Components of XFBD

Medicinal	Latin	Potential Side Effects	Allergic Reactions
麻黃	Ephedrae Herba	tachycardia, palpitations, increased blood pressure, nausea, vomiting, dizziness, strokes, seizures, sudden death, psychosis, insomnia, heatstroke, nervousness, anxiety, sweating avoid taking with MAO inhibitors	To any ephedra plant (i.e. Mormon Tea)
苦杏仁	Armeniacae Semen Amarum	dizziness, sudden fainting, palpitations, headache, nausea, vomiting, seizures, coma, cyanosis	To almonds or any component of almonds
生石膏	Gypsum Fibrosum	upset stomach, loss of appetite	To calcium sulfate, calcium or sulfates
薏苡仁	Coicis Semen	upset stomach, frequent urination, excessive sweating Use with Caution: Pregnancy	To coix seed, also known as Job's tears
苍术	Atractylodis Rhizoma	nausea, dry mouth, bad taste in mouth, upset stomach, increased gastrointestinal motility	To any plant in the genus Atractylodes , such as ragweed
广藿香	Pogostemonis Herba	nausea, upset stomach, increased gastrointestinal motility	To any plant in the Pogostemon genus (i.e. Patchouli)
青蒿	Artemisiae Annuae Herba	nausea, vomiting, upset stomach, decreased blood pressure, decreased heart rate, decreased blood sugar, increased CYP3A4 and 2B6 activity	To any Artemisiae or mugwort plant
马鞭草	Verbenae Herba	nausea, vomiting, dizziness, headache, abdominal pain Contraindicate for pregnant patients	To any Verbena plants, also known as verbena or vervain
虎杖	Polygoni Cuspidati Rhizoma et Radix	nausea, vomiting, stomach upset, abdominal pain, diarrhea, dehydration; large doses can cause liver damage and could result in leukopenia and hematuria Contraindicate for pregnant patients	To Polygonum cuspidatum , also known as Japanese Knotweed, Japanese Fleeceflower
芦根	Phragmitis Rhizoma	fatigue, loss of appetite, diarrhea	To any Phragmites , also known as common reed

葶苈子	Descurainiae Semen	nausea, vomiting, stomach upset	To Descuriania sophia also known as flixweed or tansy mustard To similar plants such as garden cress, maca or dittany
化橘红	Citri Grandis Exocarpium	large doses can lead to sore or dry throat	To the pomelo fruit or peel; citrus fruits

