8.3 Management of Side Effects

It is possible that some participants will experience transient or prolonged AEs during the study. However, it is important to note that, in this trial, the visits will be conducted remotely and hence, AEs will be assessed remotely.

Management of AEs and side effects will be by the participant's health care providers. The single exception is to stop the study medication or placebo in the event of greater than grade 1 AE. Clear instructions to participants to call 911, go to their local urgent care or emergency care center, or contact their health care provider are provided during the enrollment, consent process and by the app participants use to report symptoms.

Patients report symptoms (PRO) that include potential adverse events daily and weekly on the app. In the event, they have symptoms necessitating an encounter with the health provider, contact between the health provider by the study coordinator will be made. Participants will be given a card indicating they are on the trial and the telephone number for the study team. Participants are instructed to notify the study coordinator when they seek a health encounter. A copy of the medical records related to that encounter are to be obtained to collect additional data to appropriately grade any potential toxicity.

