8.3.1 Gastrointestinal Effects

Sore or dry mouth or throat, bad taste in mouth, loss of appetite, upset stomach, nausea, vomiting increased gastrointestinal motility, abdominal pain, diarrhea, are listed as potential side effects of the components of XFBD.

Symptom of loss of appetite (anorexia) is coded as a grade of nausea for the purposes of this trial.

Table 8.3.1 – Selected Gastrointestinal Adverse Event Grading (CTCAE)

Grade	1	2	3	4	5
Abdominal pain	Mild pain	Moderate pain; limiting instrumental ADL	Severe pain; limiting self care ADL		
Nausea	Loss of appetite without alteration in eating habits	Oral intake decreased without significant weight loss, dehydration or malnutrition	Inadequate oral caloric or fluid intake; tube feeding, TPN, or hospitalization indicated		
Diarrhea	Increase of <4 stools per day over baseline;	Increase of 4 - 6 stools per day over baseline;	Increase of ≥ 7 stools per day over baseline;	Life-threatening consequences;	Death

	mild increase in ostomy output compared to baseline	moderate increase in ostomy output compared to baseline; limiting instrumental ADL	hospitalization indicated; severe increase in ostomy output compared to baseline; limiting self-care ADL	urgent intervention indicated	
Vomiting	Intervention not indicated	Outpatient IV hydration; medical intervention indicated	Tube feeding, TPN, or hospitalization indicated	Life-threatening consequences	Death

Grade 1 abdominal pain, nausea, diarrhea and vomiting do not require treatment discontinuation. In the event of GI symptoms, the study staff should review with the participant if XFBD is being taken with food. For grade 1 side effects, participants may be referred to their primary health care providers. For grade 2 nausea the study agent may be continued. For all other grade 2 or greater events or grade 3 nausea participants are instructed to discontinue study medication or placebo and must be referred to their health care provider for management.

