8.3.2 Cardiovascular Effects

Rapid heart rate, decreased heart rate, palpitations, increased blood pressure, decreased blood pressure, dizziness, fainting, cyanosis are listed as potential side effects of the components of XFBD.

Table 8.3.2 – Selected Cardiovascular Adverse Event Grading (CTCAE)

Grade	1	2	3	4	5
Chest pain – cardiac	Mild pain	Moderate pain; pain on exertion; limiting instrumental ADL; hemodynamically stable	Pain at rest; limiting self care ADL; cardiac catheterization; new onset cardiac chest pain; unstable angina		
Cyanosis		Present			
Dizziness	Mild unsteadiness or sensation of movement	Moderate unsteadiness or sensation of movement; limiting instrumental ADL	Severe unsteadiness or sensation of movement; limiting self care ADL		
Hypertension	Systolic BP 120 - 139 mm Hg or diastolic BP 80 – 89 mm Hg;	Systolic BP 140 – 159 mm Hg or diastolic BP 90-99 mm Hg if previously WNL; change in baseline medical intervention indicated; recurrent or persistent (≥ 24 hrs); symptomatic increase by	Systolic BP \geq 160 mm Hg or diastolic BP \geq 100 mm Hg; medical intervention indicated; more than one drug or more intensive therapy than previously used indicated;	Life threatening consequences (e.g., malignant hypertension, transient or permanent neurologic deficit, hypertensive crisis); urgent intervention indicated	Death

		>20 mm Hg (diastolic) or to >140/90 mm Hg; monotherapy indicated initiated			
Hypotension	Asymptomatic, intervention not indicated	Non-urgent medical intervention indicated	Medical intervention indicated; hospitalization indicated	Life-threatening consequences and urgent intervention indicated	Death
Palpitations	Mild symptoms; intervention not indicated	Intervention indicated			
Syncope				Fainting, orthostatic collapse	

In the event of grade 1 or greater cardiovascular symptoms, the study staff must refer the participant to their primary health care providers. For grade 2 or greater events participants must be referred to their health care provider for evaluation and study agent is discontinued.

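### Mild drug effects that resemble COVID-19 may be understated in the primary safety outcome, because grade 1 recording is discretionary and app symptoms are compared by arm only as a sum

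*Combined protocol and SAP*

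**What the plan says.** The third primary outcome (10.2.1.3) is the treatment-emergent side effects and safety profile of XFBD and placebo, with no grade threshold. Section 10.6.1 plans regression models for it but does not say which events count.

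On collection, section 8.3 says: "Patients report symptoms (PRO) that include potential adverse events daily and weekly on the app".

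On recording, section 7.2 sets three triggers for an eCRF entry within 72 hours: grade 2 or higher, serious, or, in its words, "All AEs that led to a change in study treatment/intervention regardless of grade". Section 7.1 counts the participant-reported outcomes among the AE information sources and offers a one-grade worsening as an example of clinical significance, but adds: "Determination of clinical significance must be made by the medical monitor". It also places worsening of COVID-19 outside the AE definition. Section 7.3 has investigators judge causality, "indicating on the eCRF that an AE is either related or unrelated".

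On grade 1 management, section 8.3.1 says: "Grade 1 abdominal pain, nausea, diarrhea and vomiting do not require treatment discontinuation". Section 8.3.2 says: "In the event of grade 1 or greater cardiovascular symptoms, the study staff must refer the participant to their primary health care providers", with the agent stopped from grade 2. Section 8.3.4 lets the agent continue for grade 1 or 2 fatigue.

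On analysis, section 10.6.2 sums the 0-4 app ratings into a daily score and compares the 28-day AUC and weekly scores by arm. The secondary safety outcomes cover SAEs, AEs leading to discontinuation, and grade 3 and 4 AEs.

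**The concern.** When a drug side effect looks like a symptom of the disease, attribution in a single patient is weakest, and here it is made remotely. A placebo arm removes the need for that judgement, but only if each symptom is shown by arm. The plan specifies such a comparison for the sum alone, and there a drug-induced symptom that is among the scored items would count as disease severity.

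At stake is one of four primary outcomes, for a product on which section 2.2 says formal toxicity studies have not been done. A mild but common excess of, say, nausea on XFBD could appear neither in the eCRF AE data nor in any specified comparison.

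**Working it through.** **1. Which symptoms overlap, and do they meet a 7.2 trigger at grade 1?**

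| Symptom | Named as COVID-19 symptom | Named as XFBD side effect | Action at grade 1 | 7.2 trigger met |
|---|---|---|---|---|
| Nausea, vomiting, diarrhea | 2.1 | Table 8.2, 8.3.1 | Agent continues; referral optional | No |
| Dizziness | 2.1 | Table 8.2, 8.3.2 | Agent continues; referral required | No |
| Fatigue | 2.1 (with myalgia) | Table 8.2, 8.3.4 | Agent may continue | No |
| Abdominal pain | Only through the gastrointestinal class in 4.2.4 | Table 8.2, 8.3.1 | Agent continues; referral optional | No |
| Sore throat | 4.2.4 | Table 8.2, 8.3.1 | No grading row, no grade 1 stopping rule | No |
| Headache | 2.1, 4.2.4 | Table 8.2, 8.3.3 | Agent stopped at any grade | Yes |

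Each "No" holds unless treatment is in fact changed. Five symptoms are firm. Abdominal pain is inferred from the list "fever, cough, sore throat, malaise, headache, muscle pain, gastrointestinal symptoms" in 4.2.4. Sore throat is weaker because Table 8.2 ties it to dose: "large doses can lead to sore or dry throat".

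**2. What does the specified comparison do with one mild symptom?** An illustration: suppose XFBD causes a 1-point symptom for 14 days in an extra 20% of its arm. The mean 28-day AUC then shifts by 0.20 × 14 × 1 = 2.8 points. The documents give no SD for the AUC. For an assumed SD of 30 to 100 the shift is 2.8/30 = 0.09 to 2.8/100 = 0.03 SD, far too little to notice with 30 per arm.

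**3. How precise would a per-symptom table be?** The frequencies in 2.1 are taken as the rate in each arm. This is an assumption: they are combined categories at presentation, and rises after entry may be more or less common. Expected counts in 30:

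- nausea and vomiting: 0.039 × 30 = 1.2
- diarrhea: 0.048 × 30 = 1.4
- headache or dizziness: 0.121 × 30 = 3.6
- myalgia or fatigue: 0.358 × 30 = 10.7

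No frequency is given for sore throat or abdominal pain.

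The Newcombe 95% interval for a risk difference at equal counts has half-width √[(p − l)² + (u − p)²], where l and u are the Wilson limits for p.

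| Count per arm | p | l | u | Half-width |
|---|---|---|---|---|
| 1 of 30 | 0.033 | 0.006 | 0.167 | 0.136 |
| 4 of 30 | 0.133 | 0.053 | 0.297 | 0.182 |
| 11 of 30 | 0.367 | 0.219 | 0.545 | 0.232 |
| 15 of 30 (widest) | 0.500 | 0.332 | 0.668 | 0.238 |

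With about a 10-point excess, the intervals are −0.056 to 0.266 (4 v 1), −0.100 to 0.293 (7 v 4) and −0.142 to 0.327 (14 v 11).

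Exact power of a two-sided Fisher test at 0.05 for a 10-point excess is 9.2%, 9.3%, 9.5% and 7.6% at base rates of 3.9%, 4.8%, 12.1% and 35.8%. Reaching 80% power needs an excess of about 30, 31, 35 and 39 points.

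**The case against.** The best reply is that the plan has other routes to these events. Section 7.1 makes the app reports an AE source, requires review by the coordinator and medical monitor, and accepts a one-grade worsening as significant, so a new grade 1 symptom can become an AE. Section 7.3 implies a causality entry on the eCRF for every AE. The schedule in 6.1 has an AE-tracking row with five post-entry marks, and 8.3.1 has staff review intake with the participant when GI symptoms occur. Section 7.2 can also be read as a timing rule. All of this stands, and it is why the loss is possible rather than certain. None of it obliges a grade 1 record, and all of it passes through the medical monitor's judgement.

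A reader might go further and infer that any effect put down to COVID-19 can never be an AE, at any grade. The text does not settle that: 7.1 defines an AE whatever its attribution and includes new-onset events, and its exclusion concerns worsening of COVID-19.

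A reader might also infer that the app data are lost to safety, or that no useful table is possible without a pre-dose 0-4 rating. Neither follows. Ratings are collected daily. Section 10.6 (descriptive statistics by arm), exploratory objective 1.4.3 and the remark in 2.2 on symptom comparisons all leave room for a per-symptom table, though none specifies one. Randomization balances baseline symptoms in expectation, and 6.2.18 and 6.2.19 already record symptoms before entry. The rating would add the ability to show worsening of a symptom already present.

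Finally, this is an unpowered pilot whose comparisons are for planning. That limits the consequence, but documenting side effects is itself a primary outcome.

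**Conclusion.** The point holds in a limited form. For five symptoms clearly, and two less firmly, a grade 1 event need not reach the eCRF unless treatment changes. Whether it counts as an AE is discretionary, and the only specified by-arm use of the app ratings is a sum. Outcome 10.2.1.3 may therefore understate mild effects or effects attributed to COVID-19.

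The documents do not support saying that such toxicity will be missed, or how much of it. The intervals above describe the precision of the remedy, not the size of the loss, and they rest on the 2.1 frequencies as assumed rates. Only five app symptoms are visible in Appendix VI, two of which (abdominal pain and anxiety) are in Table 8.2, so the full list of rated items cannot be checked. This is a cheap improvement worth considering. The trial's conclusions do not depend on it.

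**What to change.** Add to 10.6.1 a descriptive safety table by arm, regardless of attribution, for each app symptom that also appears in Table 8.2. For each symptom give the proportion with a new or worsened report during Days 1-14 and the maximum rating, with the risk difference and its 95% CI. Take the symptoms recorded under 6.2.18 and 6.2.19 as baseline. Preferably add one 0-4 rating in the existing app before the first dose; unlike the table, it cannot be recovered later. Specify the table before the planned unblinding in 10.7.

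A sentence saying whether grade 1 AEs get an eCRF entry would also align 7.2 with 7.3, but that is only a clarification.

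The cost is one table and, if adopted, one app entry per participant. Any overlapping symptom not already in the app would have to be added. Evolving COVID-19 symptoms add noise in both arms, and with intervals of about ±14 to ±24 points the table should be labelled descriptive and carry no tests.

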8.3.1 Gastrointestinal Effects

Sore or dry mouth or throat, bad taste in mouth, loss of appetite, upset stomach, nausea, vomiting increased gastrointestinal motility, abdominal pain, diarrhea, are listed as potential side effects of the components of XFBD.

Symptom of loss of appetite (anorexia) is coded as a grade of nausea for the purposes of this trial.

Table 8.3.1 – Selected Gastrointestinal Adverse Event Grading (CTCAE)

Grade	1	2	3	4	5
Abdominal pain	Mild pain	Moderate pain; limiting instrumental ADL	Severe pain; limiting self care ADL		
Nausea	Loss of appetite without alteration in eating habits	Oral intake decreased without significant weight loss, dehydration or malnutrition	Inadequate oral caloric or fluid intake; tube feeding, TPN, or hospitalization indicated		
Diarrhea	Increase of <4 stools per day over baseline;	Increase of 4 - 6 stools per day over baseline;	Increase of ≥ 7 stools per day over baseline;	Life-threatening consequences;	Death

	mild increase in ostomy output compared to baseline	moderate increase in ostomy output compared to baseline; limiting instrumental ADL	hospitalization indicated; severe increase in ostomy output compared to baseline; limiting self-care ADL	urgent intervention indicated	
Vomiting	Intervention not indicated	Outpatient IV hydration; medical intervention indicated	Tube feeding, TPN, or hospitalization indicated	Life-threatening consequences	Death

Grade 1 abdominal pain, nausea, diarrhea and vomiting do not require treatment discontinuation. In the event of GI symptoms, the study staff should review with the participant if XFBD is being taken with food. For grade 1 side effects, participants may be referred to their primary health care providers. For grade 2 nausea the study agent may be continued. For all other grade 2 or greater events or grade 3 nausea participants are instructed to discontinue study medication or placebo and must be referred to their health care provider for management.

